## 1 Scientific Question

Can multiphase computed tomography (CT) angiography replace four-vessel angiography as a supplementary radiological examination for the determination of total brain infarction within the Swedish legal framework? An evaluation of a robust CT-Angiography protocol and a direct comparison between these radiological modalities.

## 2 Background

Total brain infarction, which is equivalent to human death, is confirmed after a two-step clinical neurological exam. This exam assesses cranial nerve functions and the individual's ability to breathe independently. In some instances, it is necessary to verify this diagnosis with a radiological method to confirm that total brain infarction has occurred. Such situations include when brain function is affected metabolically or pharmacologically, when body temperature is too low, when the cause of total brain infarction is unclear, or when injuries to the brainstem or posterior cranial fossa make clinical diagnosis difficult. Additional cases include situations where the clinical exam is incomplete, such as in cases of high spinal injury, facial injury, severe chronic obstructive pulmonary disease, chronic hypoxia, or pacemaker dependency.

In summary, a significant proportion of clinical neurological examinations need to be supplemented with a radiological examination to determine total brain infarction and establish conditions for so-called DBD donation – donation after brain death (donation after injury that has given rise to brain death). The gold standard for such radiology in Sweden is aortocranial angiography, or four-vessel angiography, a catheter-guided injection of contrast medium to demonstrate the absence of blood flow to the brain's vessels.

Four-vessel angiography can mainly be performed at regional and university hospitals by a radiologist with neuro- or vascular intervention competence and is a resource-intensive procedure. The lack of equipment and necessary competence at smaller hospitals poses challenges for performing the examination locally. Today, four-vessel angiography has essentially no indication other than determining total brain infarction, which is why the method is not part of every radiologist's competence or every hospital's routine examination.

If a patient with probable arrested circulation to the brain needs to be transported to another hospital for such an examination, difficult emotional decisions sometimes arise for next of kin and ethical decisions for healthcare providers. It also places great logistical demands on healthcare and risks constituting an obstacle to a donation process.

A consensus document from The World Brain Death Project emphasizes that additional radiological diagnostic modalities beyond four-vessel angiography may be applicable for determining total brain infarction, including radionuclide methods (Single Photon, Emission Computed Tomography, e.g., SPECT or perfusion scintigraphy) or transcranial Doppler. However, the consensus advises against CT angiography or MR angiography (MRA)/diffusion-weighted MRI (dMRI) for the time being, pending further studies demonstrating favorable sensitivity and specificity. They emphasize the need for standardized criteria adaptable to different healthcare systems. Further the consensus concludes that four-vessel angiography constitutes the reference method against which other modalities are compared in research contexts (1).

Central aspects for comparisons between methods are the methods' sensitivity and specificity. Internationally, different guidelines and regulations are applied. In Germany, for example, four-vessel angiography is not advocated due to its invasive nature (2); in the USA, CTA and MRA are advised against due to insufficient validation of the methods (3). In Polish guidelines, a combination of CT-Angiography and CT-perfusion (CTP) is recommended (4,5), whereas in French guidelines, only CT-Angiography is the recommended diagnostic modality (6,7). In Sweden, there is a binding regulation that establishes how the diagnosis of total brain infarction is to be made when the clinical examination needs to be supplemented; four-vessel angiography or radionuclide methods constitute possible alternatives (8).

A significant proportion of these patients are potential organ donors, for whom medical principles and national legislation place particularly high demands on diagnostic reliability. Furthermore, there is a need to make diagnostic methods available outside regional and university hospitals where specialized neuroradiological competence may be lacking. Against this background, SBU (Swedish Agency for Health Technology Assessment and Assessment of Social Services) investigated in 2018 the scientific basis for assessing the reliability of two alternative diagnostic methods to four-vessel angiography: CT-Angiography and dMRI. The summary conclusion of the report was that CT-Angiography was still a method under development, that there were insufficient studies with a desirable and direct comparison between four-vessel angiography and CT-Angiography, and that there were too few studies with dMRI to make an assessment (9).

The difficulties presented were that many studies included in the report used clinically established brain infarction as a reference standard for comparison with CT-Angiography, meaning that the specificity of CT-Angiography could not be assessed. Furthermore, in several patients the clinical neurological examination was inconclusive, and objections were raised that there were no consensus or clear protocols for how the examination should be applied. On behalf of the Swedish National Donation Centre, SBU produced documentation on diagnostic reliability for nuclear medicine methods for determining total brain infarction. It was stated that the diagnostic reliability of gamma camera examination with Technetium was the same as that of four-vessel angiography in adults and children over two years and constituted an acceptable substitute (10). However, we note that nuclear medicine techniques cannot compete with CT-Angiography in terms of availability, should such a practice be enabled.

The question of whether a CT protocol could replace four-vessel angiography is thus not new but has not been studied in a way that would allow the question to be clearly addressed. The main advantages of applying CT-Angiography for this purpose, in addition to increased

availability, are that the method has a very high degree of sensitivity to intravascular contrast and that robust, operator-independent protocols can be developed and distributed.

Frampas and colleagues showed in 2009 that CT-Angiography set against clinically diagnosed brain death achieves a sensitivity of approximately 86% when applying a four-point protocol including measurement points at four cortical segments of the middle cerebral artery as well as central cerebral veins, with a specificity of 100% i.e., absence of false positive outcomes (11). Taylor and colleagues conducted a meta-analysis in 2014 of available studies on the sensitivity of CT-Angiography in confirming clinically established cessation of circulation to the brain. The ten included studies yielded a sensitivity estimate of 0.85 for a four-point evaluation as above, concluding that the method could not be recommended as a mandatory element in confirming brain death (12).

In a study by Garret and colleagues which, among other things, directly compared CT-Angiography against four-vessel angiography, a sensitivity of 75% and a specificity of 100% was reached; they stated that the low sensitivity could likely be attributed to an intradural "stasis filling", i.e., pendulum filling without sustaining circulation, and that the high specificity is far more important, i.e., the absence of false positive outcomes (that ceased circulation is determined in a patient where circulation has not ceased) (13). Suarez-Kelly and colleagues conducted a direct comparison between CT-Angiography and a nuclear medicine perfusion test, i.e., a method accepted in Sweden as a substitute for four-vessel angiography. They found that if a quantitative analysis of opacification at CT-Angiography (<80 Hounsfield units) was performed in the vessel segments M1, A1, and BA, sensitivity could be increased to 97%, with a specificity of 100% (14).

Although The World Brain Death Project states that CT-Angiography cannot replace four-vessel angiography at present (1), there is strong international support for a transition. Thomas and colleagues presented a consensus document in the UK in 2023, arguing that the examination shows 100% specificity with respect to clinically established cessation of circulation to the brain and that the 85% sensitivity is acceptable, as the method represents a safe standard that prioritizes specificity over sensitivity (15). In summary, the four-point protocol shows 100% specificity for clinically established cessation of circulation to the brain and compared with nationally accepted methods, can thus achieve 97% (14).

## 3 Project Description

### 3.1 Overall purpose and conditions of the project

We intend to establish and evaluate a new, robust protocol for CT-Angiography to determine total brain infarction. The protocol will methodologically mirror four-vessel angiography, with radiological review of cessation of intradural blood flow incompatible with life. The protocol, which differs significantly from recent recommendations regarding how such a protocol could be designed (15), is intended to be readily available in all modern CT scanners.

The protocol's performance is compared with four-vessel angiography as a confirmatory test for determining cessation of circulation after clinical diagnostics, first in a local, smaller study at Karolinska University Hospital and, in the next step, in a national multicenter study, with the goal of achieving "non-inferiority". Computed tomography angiography is performed according to a clinically standardized protocol, with contrast dose and administration fully in

accordance with CE marking requirements. The study intends to elucidate key aspects of establishing novel ROIs in computed tomography and is to be equated with an interrater assessment study.

In parallel, we also intend to study the patient-near ultrasound modality, Transcranial Doppler (TCD), regarding its predictive and diagnostic performance for this purpose.

The timeline for the pilot study depends on the number of patients cared for in the intensive care units at Karolinska University Hospital, Solna, with suspected total brain infarction requiring confirmation by four-vessel angiography.

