### **Conventional Four-Vessel Angiography:**

- Two consecutive four-vessel angiographies are performed with at least 30 minutes in between.
- Images are saved locally in the Karolinska Picture Archiving and Communication System (PACS).
- Date and time for established outcome (positive or negative examination).

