### **Processing of Computed Tomography Angiography:**

- The validity of the X-ray examination is tested by reviewing the entire series and confirming that it meets the requirements for contrast filling of extracranial vessels.
- Two board certified neuroradiologists will conduct an initial training session determining allowed contrast filling over the phases.

- Following a washout period of a minimum of two weeks, the neuroradiologists will independently re-review all images and determine a binary outcome of cessation of blood flow compatible with brain death in the same manner as the four vessel angiography is evaluated.
- After an additional wash out period of a minimum of four weeks the images will be independently re-reviewed.
- Following the two reading sessions inter- and intrarater agreements will be determined and comparison to gold standard test will be performed.

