## **5. Clinical Relevance, Patient and Societal Benefit**

The study's overall goal is to establish a protocol for CT-Angiography as a simple, robust, and accessible radiological modality for confirming total brain infarction when such confirmation is needed, with diagnostic performance comparable to four-vessel angiography. If such were to gain medical and medico-legal support, great gains stand to be made. The study has the potential to establish a basis for future care processes to determine total brain infarction outside regional and university hospitals. This creates conditions for more equal care. The project also has the potential to increase the likelihood of DBD donations and more

transplants. In addition to significant health gains for those who can receive transplants, substantial economic gains can be achieved. A health economic study from the Department of Clinical Sciences, Lund 2015 (referenced in SOU 2015:84) showed that an increase of 100-150 donors annually in Sweden can lead to savings of 70-80 million kronor annually, only regarding the number of donated kidneys, additionally possibility for savings of 70% per transplanted patient (of expected costs without kidney transplantation) (17).

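### The goal of non-inferiority to four-vessel angiography cannot be met by a design that uses four-vessel angiography as the reference standard; the planned analyses can show agreement only

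*Protocol*

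**What the plan says.** Section 3.1 (Overall purpose and conditions) compares the performance of the new CT protocol with four-vessel angiography, first in a local study and then "in a national multicenter study, with the goal of achieving 'non-inferiority". The goal can be read as covering both stages, but it attaches most directly to the national one. Section 5 gives the overall aim as a CT protocol "with diagnostic performance comparable to four-vessel angiography".

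The same test is also the yardstick. Section 2 states: "The gold standard for such radiology in Sweden is aortocranial angiography, or four-vessel angiography". It also reports an international consensus that "four-vessel angiography constitutes the reference method against which other modalities are compared in research contexts". In section 3.6, the processing of the CT images ends with "comparison to gold standard test will be performed", and the statistical analyses determine CT sensitivity and specificity in relation to four-vessel angiography. Section 3.10 lists descriptive statistics, rater reliability, sensitivity, specificity and predictive values, and nothing else.

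**The concern.** A non-inferiority or comparability claim about two diagnostic tests says that one is about as accurate as the other. To support it, both tests must be scored against something other than either of them. Here the comparator is also the reference, so its own accuracy is fixed at 100% and is never estimated.

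What is at stake is the wording of the conclusion. The project asks whether CT may replace a test used to determine death. A report that CT was non-inferior, or performed comparably, would be read as a finding about relative accuracy. The planned analyses can only show how often CT gives the same answer as four-vessel angiography.

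**Working it through.** **The plan's own figure.** The only relevant figure is the total of about 250 examinations in section 3.5. It equals about 50 local plus 200 national (section 3.3). No margin, error rate or expected accuracy is given there, so it cannot be derived further. The point does not depend on it.

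**Step 1: what the planned scoring does.** Cross-classify patients by CT and four-vessel angiography (4V):

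| | 4V positive | 4V negative |
|---|---|---|
| CT positive | a | b |
| CT negative | c | d |

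- CT sensitivity = a/(a+c); CT specificity = d/(b+d).
- 4V sensitivity against itself = (a+c)/(a+c) = 1; 4V specificity against itself = (b+d)/(b+d) = 1.
- Difference, CT minus 4V: −c/(a+c) for sensitivity and −b/(b+d) for specificity. Neither can be positive. CT can tie or lose, and all b + c disagreements are charged to CT.

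**Step 2: what a non-inferiority test becomes.** With any margin m, the requirement that CT sensitivity exceed 4V sensitivity minus m reduces to CT sensitivity > 1 − m. The same holds for specificity. This is a one-sample performance limit on agreement, not a comparison of two accuracies, and no choice of m changes that.

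**Step 3: is another standard planned?**
- Clinical examination: it is the route into the study (section 3.6), so it does not separate the patients independently.
- Transcranial Doppler: section 3.1 studies it as a further test, not as a reference.
- Second angiography: "Two consecutive four-vessel angiographies are performed with at least 30 minutes in between". This repeats the same test.
- Radionuclide methods: section 2 describes them as accepted in Sweden, but they are not part of the study procedures.
- Section 3.10 names no analysis that scores both tests against a third standard.

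**Step 4: hypothetical illustration of the logic.** The protocol gives no error rate for four-vessel angiography, so these inputs are assumptions and not estimates. Let 4V have true sensitivity 0.98 and specificity 0.95, let 90% of patients truly have ceased circulation, and let CT be perfect.
- 4V positive: 0.90×0.98 + 0.10×0.05 = 0.887. Apparent CT sensitivity = 0.882/0.887 = 0.994.
- 4V negative: 0.10×0.95 + 0.90×0.02 = 0.113. Apparent CT specificity = 0.095/0.113 = 0.841.
- With the true share at 80% or 95%, apparent specificity is 0.922 or 0.714.

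A better CT is recorded as worse. Conversely, a CT that copied every 4V error would score 100% on both measures. If 4V is taken as error-free, agreement and accuracy coincide and Step 2 is all that remains.

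**Step 5: what an agreement limit would look like (illustration).** The protocol does not state the reference-positive share. Assume 80%, 90% or 95% of the 200 national patients. With zero false positives among n reference-negatives, the exact (Clopper-Pearson) two-sided 95% lower limit is 0.025^(1/n):

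| Assumed positive share | Reference-negatives n | Lower limit for specificity |
|---|---|---|
| 80% | 40 | 0.91 |
| 90% | 20 | 0.83 |
| 95% | 10 | 0.69 |

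These limits bound agreement with four-vessel angiography among its negatives. They say nothing about which test is right when the two disagree.

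**The case against.** The strongest reply is that four-vessel angiography is the operative standard under the Swedish rules, so agreement with it is exactly what matters. The project's question (sections 1 and 3.5) is framed within that legal setting, and the planned analyses already measure agreement. The word non-inferiority appears once, in the protocol's own quotation marks, mainly about a study planned preliminarily for 2029. On this view it is loose terminology.

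Much of this stands: agreement is a sound target, and no analysis has to be replaced. It does not rescue the stated goal. If the reference is treated as error-free, the goal becomes a minimum specificity and sensitivity, and the protocol should say so. Section 5 repeats the comparability aim without any such qualification.

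A reader might infer more than the documents support:

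- **That disagreements are probably errors of four-vessel angiography.** Section 2 says of CT that "the method has a very high degree of sensitivity to intravascular contrast", and reports a study that "directly compared CT-Angiography against four-vessel angiography, a sensitivity of 75% and a specificity of 100% was reached". But section 2 attributes that low sensitivity to stasis filling, which it describes as filling without sustaining circulation. On that account circulation had ceased and CT gave the false negatives.
- **That the true accuracy difference could be large in either direction.** With an assumed 180 positives among 200 and 75% sensitivity there would be 45 disagreements, or 45/200 = 22.5 points. A gain of that size for CT would need four-vessel angiography to be wrong in all 45. This is a logical extreme that section 2's explanation contradicts.
- **That section 3.5 is in error for giving no expected positive and negative counts, or that a missing margin is the fault.** Such detail may stand in a statistical analysis plan that is not shown.
- **That the data could never support anything beyond agreement.** Transcranial Doppler, EEG and MRI results are recorded (sections 3.6 and 3.8). None is planned as a reference, so the limitation is one of the planned analyses.

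**Conclusion.** The point holds as a mismatch between the stated goal and the design. Sections 3.1 and 5 promise non-inferior or comparable performance, while sections 2 and 3.6 make the comparator the reference. The planned analyses can therefore show agreement with four-vessel angiography and cannot show relative accuracy.

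This conclusion follows from the text and the algebra and needs no numerical assumption. It has no size in percentage points, because the protocol gives no information on the error rate of four-vessel angiography. The specificity limits of 0.69 to 0.91 are illustrations that rest on an assumed reference-positive share of 95% to 80% among 200 patients and on zero false positives.

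Severity is minor to moderate. The data collection and the planned measures are sound for the legal question; the wording of the goal and of the eventual conclusion is not.

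**What to change.** 1. In section 3.1, replace the non-inferiority goal with: the goal of meeting preset minimum specificity (primary) and sensitivity against four-vessel angiography, each judged by the lower limit of the exact two-sided 95% confidence interval. Putting specificity first follows section 2, which ranks the absence of false positives above sensitivity.
2. In section 5, replace "with diagnostic performance comparable to four-vessel angiography" with agreement with four-vessel angiography that meets those preset limits.
3. Word the conclusions of both studies in the same terms.

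The numerical limits can be set in the protocol or in the statistical analysis plan, provided they are fixed before the data are seen.

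The cost is a few sentences. They can be changed before the supplementary ethics application that section 3.2 plans ahead of the national study. No additional patients, tests or changes to procedures are needed. The downside is a weaker headline claim.

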### **3.2 Study Center**

**The local study** is conducted at the Department of Perioperative Medicine and Intensive Care, in collaboration with the Department of Neuroradiology, Karolinska University Hospital, Solna.

**The national multicenter study** is coordinated by the study group at Karolinska University Hospital, Solna. We intend to include university hospitals that conduct neurointensive care and possess high neuroradiological competence, such as Gothenburg, Lund, Linkoping, Umea, Uppsala, and Orebro. A supplementary ethical application will be submitted upon completion of the pilot study, before recruiting additional national study centers.

### **3.3 Study Period and Project Plan**

A recent trend towards a larger proportion of donation processes going to DCD (Donation after Circulatory Death) carries the risk of reducing the number of potential research subjects for assessment. We need to consult with next of kin in a challenging situation, which can further affect the recruitment of research subjects. Over the past few years, approximately 15 four-vessel angiographies have been performed annually in our hospital. We believe that a sufficient study basis for statistical comparison of diagnostic performance in a local pilot study can be achieved with approximately 50 patients, during a timeframe of three years. Upon a favorable outcome of this pilot study, we intend to move the project into a second phase, in which the corresponding question is studied within the framework of a national multicenter study with far more patients, providing a stronger statistical foundation.

**Local study:** Patient inclusion is planned from December 2025, or as soon as the ethical application allows. Patient inclusion is planned to continue through December 2028, given an annual decline in the number of examinations. The goal is to recruit approximately 15 patients each year, totaling approximately 50 examinations. An interim analysis is planned after approximately eight examined research subjects, to inform decision-making regarding the reduction and selection of the number and/or phases (image sequences) to be included in the final protocol.

**National multicenter study:** Study start is planned preliminarily for May 2029 and will continue until May 2032 with an ambition to recruit a total of 200 additional patients.

